## 12.4 Lipid Management Goals Based on Risk Assessment

Principle of the			Additional	Lipid Control (mg.	
Therapeutic Strategy	Category	Absolute Risk †	Risk ‡	LDL-C	HDL-C
Primary prevention (No history of CAD)	I	< 0.5%	No	< 160	
Drug treatment should be considered after first	t I II	< 0.5%	Yes	< 140	
improving the patient's lifestyle.		≥ 0.5%, < 2.0%	No		
	III	$\geq 0.5\%, < 2.0\%$	Yes	< 120	> 40
	111	≥ 2.0%	No/ Yes	120	≥ 40
Secondary prevention (History of CAD) Drug treatment should be considered, together with improving the patient's lifestyle.		History of CAD		< 100	

†Absolute Risk is defined as Probability of death form CAD in 10 years based on NIPPON DATA 80

Revised JAS Guidelines, 2012 version (The Japan Atherosclerosis Society)

‡ Additional Risk are defined as 1) Hypo HDL-cholesterolemia (HDL-C < 40 mg/dL), 2) Family history of premature CAD in first-degree relatives (a man aged < 55 years or a woman aged < 65 years), 3) Impaired glucose tolerance. Patient who has diabetes mellitus, chronic kidney disease (CKD), non cardio-embolic stroke or peripheral arterial disease (PAD) are definded as category III

**Protocol/Amendment No.:** 832-01

#### 12.5 Diet and Alcohol

#### Diet

Patient should follow the nutrient recommendation provided by the JAS2012 for prevention of atherosclerotic cardiovascular diseases throughout this study.

- 1) with consideration for energy intake and amount of physical examination, maintain normal body weight ([Height(m)]×22)
- 2) control energy rate of fat 20 to 25%, unsaturated fatty acid 4.5% to not more than 7%, and amount of cholesterol intake, <200 mg/day
- 3) increase n-3 poly unsaturated fatty acids intake
- 4) control energy rate of carbonhydrates 50 to 60%, and increase fiber intake
- 5) control salt intake 6 g/day
- 6) limit alcohol intake <25 g/day

## Alcohol

The amount of 25 g alcohol is defined as follows:

Alcohol	25 g/day		
Beer	1 bottle (633 ml/bottle)		
Sake	180 ml		
Whiskey / Brandy	2.5 glasses (Single)		
Distilled spirit	90 ml		
Wine	2 glasses		

**Protocol/Amendment No.:** 832-01

## 12.6 Standard Operating Procedure for Liver and Muscle Enzyme Evaluations

Every increase in ALT, AST, and/or CK above the limits described in the protocol (i.e., ALT/AST  $\geq$ 3 times the upper limit of normality [ULN], and CK  $\geq$ 5 times ULN), the central laboratory will alert the investigators/ coordinators and the SPONSOR clinical personnel. The study and central laboratory SOP calls for immediate repeat testing within 3 days every time these tests reach these limits or are otherwise questionable.

Under these circumstances, the investigators/coordinators must recall the subject and attempt to identify the cause of the elevation. This evaluation should include:

## A. For CK Increases

- 1. Patients should return to the center within 3 days after result available for the following (history can be obtained over the phone in the interim):
  - A search for potential drug interactions with known inhibitors or substrate of cytochrome P-450 CYP3A4.
  - · Rule out myocardial ischemia as a cause for the elevation.
  - Documentation of unusual and/or strenuous physical activities, recent trauma, or IM injections preceding the blood testing.

#### 2. Actions

- Patients with persistent (2 or more) CK elevations between 5 and <10 times the ULN and muscle symptoms will also be discontinued.
- Patients with persistent (2 or more) CK elevations between 5 and <10 times the ULN without symptoms may remain on drug (at the discretion of the SPONSOR medical monitor) with more intensive monitoring (as agreed to by the monitor and investigator). These patients should remain on drug until repeat labs are obtained.
- Patients with persistent (i.e., 2 consecutive measurements), unexplained 10 fold elevation in CK with or without symptoms will be discontinued from the study.

NOTE: All discontinued patients should be monitored and have repeat lab draws completed until critical elevations have resolved.

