# 5.8 Subject Withdrawal/Discontinuation Criteria

Subjects may withdraw consent at any time for any reason or be dropped from the trial at the discretion of the investigator should any untoward effect occur. In addition, a subject may be withdrawn by the investigator or the Sponsor if enrollment into the trial is inappropriate, the trial plan is violated, or for administrative and/or other safety reasons. Specific details regarding discontinuation or withdrawal procedures are provided in Section 7.1.4 – Other Procedures.

Table 2 provides reasons why a subject must be discontinued from treatment but may continue to be monitored in the trial, as well as reasons why a subject must be discontinued from treatment and the trial.

Table 2 Discontinuation Scenarios

Reason for Discontinuation Scenario	Action				
The subject or legal representative (such as a parent	Discontinuation from Treatment and Trial				
or legal guardian) withdraws consent.					
The subject's treatment assignment has been	Discontinuation from Treatment and Trial				
unblinded by the investigator, Merck subsidiary or					
through the emergency unblinding call center					
Consecutive (2 or more measurements) elevations in	Discontinuation from Treatment and Trial				
ALT and/or AST $\geq 3 \times ULN$					
Consecutive elevations in CK $\geq$ 10 x ULN with or	Discontinuation from Treatment and Trial				
without muscle symptoms.					
Consecutive elevations in CK $\geq$ 5 to <10 x ULN	Discontinuation from Treatment and Trial				
with muscle symptoms.					
Subject requiring any treatment with cyclosporine	Discontinuation from Treatment and Trial				
or fibrates.					
Pregnancy (Positive serum pregnancy test): A	Discontinuation from Treatment and Trial				
positive urine pregnancy test requires immediate					
interruption of study drug while awaiting results of					
serum pregnancy (β-hCG) test.					
Any subject who is unblinded to treatment regimen	Discontinuation from Treatment and Trial				
during study. (The subject's treatment assignment					
has been unblinded by subject him/herself.)					
Adverse experiences: Subject may be withdrawn	Discontinuation from Treatment and Trial				
from the study in the event that the investigator					

04REM Confidential

Protocol/Amendment No.: 832-01

Reason for Discontinuation Scenario	Action
assesses that administration of the study drug should	
be discontinued due to the occurrence of adverse	
experiences which would interfere with study	
continuation.	

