## 2. Action

· Values of ALT or AST  $\geq$ 3 X ULN at any visit will result in mandatory retest within 3 days. Persistent (2 consecutive measurements) 3-fold elevations in ALT or AST will result in withdrawal of the patient from the study.

**Protocol/Amendment No.:** 832-01

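### Appendix 12.6 limits the CK ≥10 × ULN stopping rule to unexplained elevations, while Table 2 requires discontinuation with no condition on cause

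*Combined protocol and SAP*

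**What the plan says.** **Section 5.8, Table 2.** The lead-in covers two kinds of reason: those for stopping treatment with monitoring still possible, "as well as reasons why a subject must be discontinued from treatment and the trial". The row at issue begins "Consecutive elevations in CK $\geq$ 10 x ULN with or" and continues to cover subjects without muscle symptoms. Its action is discontinuation from both treatment and trial. It has no condition on cause.

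**Appendix 12.6, opening and A.1.** At CK ≥5 × ULN the central laboratory alerts the site and the sponsor's clinical personnel, and the test is repeated within 3 days. Then "the investigators/coordinators must recall the subject and attempt to identify the cause of the elevation". The CK work-up covers drug interactions, myocardial ischemia, strenuous activity, recent trauma and intramuscular injection.

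**Appendix 12.6, A.2.** The action for the highest CK level is: "Patients with persistent (i.e., 2 consecutive measurements), unexplained 10 fold elevation in CK with or without symptoms will be discontinued from the study". The two other action bullets cover only 5 to <10 × ULN. One of them says that asymptomatic patients in that band "without symptoms may remain on drug (at the discretion of the SPONSOR medical monitor) with more intensive monitoring".

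**The concern.** The same stopping rule appears twice, once without a condition on cause and once with one. The conditional version sits in the procedure a site follows when a CK alert arrives, and it comes straight after the instruction to look for a cause. A site doing that work-up will sort cases into explained and unexplained, and will then find a stopping instruction for only one of the two. A rise traced to a drug interaction, the first cause that A.1 lists, would literally count as explained.

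What is at stake is subject safety: a subject on a statin with a confirmed CK ≥10 × ULN could stay on study drug although Table 2 requires a stop.

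**Working it through.** The plan states no figure for this, so the main check is a comparison of texts.

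**Step 1. Compare all three enzyme stopping rules.**

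| Rule | Table 2 | Appendix 12.6 | Cause condition |
|---|---|---|---|
| Consecutive ALT and/or AST ≥3 × ULN | Stop treatment and trial | B.2: "Persistent (2 consecutive measurements) 3-fold elevations in ALT or AST will result in withdrawal of the patient from the study" | None in either |
| CK 5 to <10 × ULN with muscle symptoms | Row beginning "Consecutive elevations in CK $\geq$ 5 to <10 x ULN": stop treatment and trial | A.2: "Patients with persistent (2 or more) CK elevations between 5 and <10 times the ULN and muscle symptoms will also be discontinued" | None in either |
| CK ≥10 × ULN, with or without muscle symptoms | Stop treatment and trial | A.2: stop if unexplained | Only in 12.6 |

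Two of the three rules agree. Only the one at the highest CK level differs.

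**Step 2. Work through the cases for two consecutive CK values ≥10 × ULN.**

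- No cause found: Table 2 says stop and 12.6 A.2 says stop. They agree.
- Cause found: Table 2 says stop and 12.6 A.2 states no action. They differ.

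**Step 3. Look for text that reconciles them.** None was found. *Unexplained* is not defined, and neither place says which prevails. The only remain-on-drug provision in A.2 is for asymptomatic CK 5 to <10 × ULN, so it does not reach this case.

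**Step 4. Check the ordering inside 12.6.** A symptomatic subject with repeated CK at 7 × ULN and a known cause is discontinued. A subject with repeated CK at 12 × ULN and a known cause has no stated action. A deliberate exception would be unlikely to run that way, which points to a drafting slip in the appendix.

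**Step 5. Size of the affected group.** Two inputs are needed and the documents give neither, so both are assumptions. Let p be the share of subjects with two consecutive CK ≥10 × ULN (0.1% to 1%), and f the share of those with an identified cause (25% to 75%). With 306 subjects randomized:

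- expected number = 306 × p × f
- chance of at least one = 1 − (1 − p × f)^306

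| p | f | Expected | Chance of at least one |
|---|---|---|---|
| 0.1% | 25% | 306 × 0.00025 = 0.08 | 7% |
| 0.5% | 50% | 306 × 0.0025 = 0.77 | 54% |
| 1% | 75% | 306 × 0.0075 = 2.3 | 90% |

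This is the chance that an explained case arises at all. The chance that a site would then overlook Table 2 cannot be estimated from the documents.

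**The case against.** The strongest reply is that nothing here overrides Table 2. It is mandatory and sits in the body of the protocol, and an appendix that is silent on explained cases does not cancel it. A site can comply with both texts by following Table 2. That stands. A reader might infer that 12.6 permits explained cases to continue, or that the two texts contradict each other. The documents do not support either inference: 12.6 never says such cases may stay on drug.

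Several safeguards also reduce the risk:

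- The sponsor will already have been alerted before any decision on a confirmed CK ≥10 × ULN.
- Exclusion 14 bars cyclosporine, systemic azoles, macrolides and protease inhibitors. Section 5.5 keeps those bans in force during the trial and requires the investigator, sponsor and subject all to agree before trial therapy continues.
- Exclusion 23 bars vigorous exercise regimens, and Section 5.7.2 carries that through the study. Exclusion 25 removes subjects with earlier myopathy or rhabdomyolysis on ezetimibe or a statin.
- Table 2 has further stopping rows for cyclosporine or fibrate use, for adverse experiences, and for conditions that place a subject at unnecessary risk.

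These make an error unlikely, but they do not make the two texts agree. The adverse-experience and unnecessary-risk rows depend on judgement, whereas the CK row is a fixed threshold meant to leave none. The sponsor alert does not say what action follows.

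It is also fair to say that the documents do not prove which wording is the slip. The agreement of the other two rules favors Table 2, and so does its mandatory force.

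**Conclusion.** The inconsistency is real and worth correcting, and its expected effect is small. Appendix 12.6 A.2 states a narrower stopping rule than Table 2 and leaves explained, confirmed CK ≥10 × ULN without an action. Under the assumed rates, between 0.08 and 2.3 of 306 subjects would fall in that gap. The range is wide because neither input comes from the documents. The finding itself rests only on the wording.

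Two wider readings should be resisted. First, a reader might infer a threat to the efficacy result. There is none: the hypotheses and the alpha rule do not use this criterion, the Tier 1 CK endpoints in Table 5 are defined by CK level and not by explanation, and even 2.3 subjects is small beside the planned allowance of 306 − 279 = 27 for discontinuation. Second, a reader might infer that events of clinical interest would go unreported, because Section 7.2.3.2 item 3 refers to a CPK discontinuation criterion without saying where it is. Table 2 supplies that criterion, and myopathy and rhabdomyolysis are reportable in their own right, so the missing cross-reference is only editorial.

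**What to change.** In Appendix 12.6 A.2, delete *unexplained* and state the threshold as Table 2 does, for example: *Patients with CK ≥10 × ULN on 2 consecutive measurements, whether or not they have symptoms, will be discontinued from the study.* Keep the A.1 cause work-up as it is, since it guides clinical care whatever the stopping decision.

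If the sponsor did intend an exception for explained elevations, Table 2 has to carry it, and 12.6 has to define the term and state the action. Deletion is the simpler and more cautious choice.

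The cost is one sentence and a memo to sites, with no change to the analysis or sample size. The downside is that a few subjects with a benign explanation are stopped, but Table 2 already requires that. Adding a pointer from Section 7.2.3.2 item 3 to Table 2 is optional tidying.

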#### B. For ALT or AST Increases

- 1. Patients should return to the center within 3 days after results available for the evaluations listed below (history can be obtained over the phone in the interim). In cases where the ALT and/or AST value is ≥3-fold ULN patients should generally remain on drug until the follow-up visit.
  - · Careful questioning of recent alcohol consumption. Recent change in pattern.
  - Search for iatrogenic causes of hepatitis and liver injuries (acetaminophen, amiodarone, aspirin, chlorpromazine, dantrolene, erythromycin, halothane, isoniazid, methyldopa, nitrofurantoin, oxyphenisatin, perhexiline maleate, phenytoin, propylthiouracil, rifampin, sulfonamides, tetracyclines).

MK-0653H-832-01 Final Protocol

**Protocol/Amendment No.:** 832-01

• Search for alternative medical causes such as cholelithiasis and ascending cholangitis, viral illnesses, hepatitis, or potential exposure to viral hepatitis (transfusion).

## 2. Action

· Values of ALT or AST  $\geq$ 3 X ULN at any visit will result in mandatory retest within 3 days. Persistent (2 consecutive measurements) 3-fold elevations in ALT or AST will result in withdrawal of the patient from the study.

**Protocol/Amendment No.:** 832-01

## 12.7 Clinical Study Conduct System

Clinical study conduct system in Japan is provided by Japanese language.

Protocol/Amendment No.: 832-01

